## PROTOCOL SUMMARY

Title:	Energy Metabolism in Thyroidectomized Patients
Protocol Number:	HM20016169
IND Sponsor:	Not applicable.
Principal Investigator /Study Chair/Coordinating Center/Sponsor-Investigator:	[name].
Study Sites:	
Virginia Commonwealth University Division of Endocrinology Diabetes and Metabolism Department of Internal Medicine [name]
 
Virginia Commonwealth University Health System Clinical Research Services Unit North Hospital 8th floor [name]

Clinical Trial Phase:	Pilot Study
Study Disease:	Surgical hypothyroidism, Weight gain, Energy Expenditure
Main	
Eligibility Criteria:	
Age ≥18-89 years of age Clinical indication for total thyroidectomy TSH at screening >0.45 <4.5 mIU/ml Total Thyroidectomy for benign goiter or thyroid cancer not requiring suppressive thyroid hormone therapy Ability to understand and the willingness to sign a written informed consent document.

Primary Objectives:	To characterize changes in energy metabolism following thyroidectomy in response to LT3/LT4 vs. LT4 therapy.

We will perform dense phenotyping including energy expenditure and substrate utilization during a up to 24-hour stay in a whole-room indirect calorimeter before, and at three and six months following the surgery. These data will enable us to define in detail the changes in weight and energy metabolism due to the lack of endogenous thyroid hormone production, and the response to LT3/LT4 therapy.

**Secondary Objectives:**

**To determine the effects of thyroidectomy and response to therapy on cardiovascular and endothelial function.**

This aim will provide novel information on the effects of hypothyroidism on cardiovascular function, in a well-defined experimental model, and of the potential for LT3/LT4 therapy in preventing hypothyroidism-associated myocardial dysfunction and excess of cardiovascular risk.

**Tertiary Objectives**

**To characterize the changes in lipid metabolism following thyroidectomy.** In this aim, we will be able to define the changes in serum lipids as a consequence of post-surgical hypothyroidism, and to estimate whether LT3/LT4 is superior to LT4 therapy with respect of this important endpoint associated with cardiovascular risk.

**Endpoints:**

**Primary.** Differences in weight between LT4 alone or LT3/LT4 therapy.

**Primary.** Differences in Energy Expenditure between LT4 alone or LT3/LT4 therapy.

**Secondary.** Differences in echocardiogram parameters between LT4 alone or LT3/LT4 therapy.

**Secondary.** Differences in Lipid levels between LT4 alone or LT3/LT4 therapy.

**Exploratory.** Effects of the Thr92Ala D2 variant on the primary and secondary endpoints.

**Exploratory.** Differences in QoL (ThyPRO-39) between LT4 alone or LT3/LT4 therapy.

**Study Design:**

**This is a pilot, randomized, double-blind, controlled, parallel study** in which thirty patients will be phenotypically characterized at baseline before surgery, 3 and 6 months following surgery. There will be one 6 week post-surgery dose adjustment visit. Both groups will receive active therapy for the treatment of hypothyroidism: either LT4 and placebo or LT4/LT3 combination therapy.

**Study Intervention Description:**

**Agent/** Levothyroxine and placebo or Levothyroxine/Liothyronine combination.

**Number of Subjects:** 30

**Subject Participation Duration:** 6 Months

**Estimated Time to Complete Enrollment:** 1 year

**Statistical Methodology:**

Our preliminary estimate is based on the findings of our cross-over study with a population of 14 patients (13 female, weight (kg) =  $69.7 \pm 12.5$ , age (years) =  $49.3 \pm 8.0$ ). After substitution of LT3 for LT4 a decrease in weight was  $1.8 \pm 1.9$  kg, and in LDL-cholesterol was 13%. In this study LT3 treatment resulted in 85% higher morning serum T3 level as compared to LT4. From our recent study, the estimated increase in serum T3 level on LT3/LT4 combination therapy adopted in the current proposal would be about 44% as compared to LT4 alone, approximately half of the increase in serum T3 observed with full LT3 substitution. Using the point estimates of our recent meta-analysis, the predicted weight gain occurring after thyroidectomy is 1.4 to 2.2 Kg. Similarly, no study has measured changes in energy expenditure using WRIC in similar study populations, and our crossover intervention did not show significant differences in REE between LT3 only and LT4 treatments despite a significant change in body weight.

We hypothesize that LT3/LT4 therapy will be superior to LT4, likely to a smaller effect than LT3 alone. We do not expect that the effect would be larger than that of pure LT3 therapy. On the other hand, the complex interaction of LT4 and LT3 means that an optimal combination ratio may exist theoretically that outperforms the pure LT3 therapy. Based on our empirical observations and extrapolations, we enumerate a few possible effect size to estimate the required sample sizes in a two-arm, randomized, cross-sectional design, given a significance level of 0.05. The following sample size calculation and statistical power estimation are obtained based on two-sample, one-sided t-test based on weight loss in LT3/LT4 as compared to LT4 alone.

Weight Loss LT3/LT4	SD (kg)	Power (%)	Sample Size per	Weight Loss LT3/LT4	SD (kg)	Power (%)	Sample Size per
1.4	1.9	62.7	15	1.4	1.9	80.8	24
1.6	1.9	72.7	15	1.6	1.9	81.6	19
1.8	1.9	81.2	15	1.8	1.9	81.2	15
2.0	1.9	87.8	15	2.0	1.9	80.3	12
2.2	1.9	92.6	15	2.2	1.9	80.1	10
1.4	2.3	49.3	15	1.4	2.3	80.9	35
1.6	2.3	58.5	15	1.6	2.3	81.0	27
1.8	2.3	67.2	15	1.8	2.3	80.2	21
2.0	2.3	75.1	15	2.0	2.3	81.9	18
2.2	2.3	81.9	15	2.2	2.3	81.9	15

**Power and sample size calculation for weight differences following thyroidectomy between LT4 and LT4/LT3 combination therapy. The left columns indicate the power of the study on the current sample size (dictated by the time and funding constrains of the R21 funding mechanism). The right columns indicate the sample size calculations necessary to assure an 80% power with a significance of 0.05.**

Similarly, power and sample size calculations for changes in lipids were based on our original cross-over study which was associated with 13% reduction in LDL and 12% reduction in non-HDL. From our preliminary study, the estimated increase in serum T3 level on LT3/LT4 combination therapy would be about 44% as compared to LT4 alone. With linear extrapolation, a 5% to 8% reduction in LDL or non-HDL for this study is hypothesized. We also provide the sample size calculation and power estimation for the hypothesized percent reduction in LDL/non-HDL given the LDL of  $122.6 \pm 25.2$  (mg/dl) for LT4 group.

% reduction in LDL LT3/LT4 vs LT4	SD (%)	Power (%)	Sample Size per Arm	% reduction in LDL LT3/LT4 vs LT4	SD (%)	Power (%)	Sample Size per Arm
5%	10	49.7	15	5%	10	80.4	34
6%	10	62.6	15	6%	10	80.7	24
7%	10	74.2	15	7%	10	81.0	18
8%	10	83.5	15	8%	10	81.1	14
5%	12	39.9	15	5%	12	80.7	49
6%	12	49.7	15	6%	12	80.4	34
7%	12	60.5	15	7%	12	80.2	25
8%	12	70.5	15	8%	12	81.4	20

**Power and sample size calculation for differences in LDL-cholesterol following thyroidectomy between LT4 and LT4/LT3 combination therapy. The left columns indicate the power of the study on the current sample size (dictated by the time and funding constrains of the R21 funding mechanism). The right columns indicate the sample size calculations necessary to assure an 80% power with a significance of 0.05.**

Given the sample size of 15, we further estimate the statistical power of detecting differences in energy expenditure. Based on our recent pilot study on assessing resting metabolic rate (RMR) across 12 healthy, normal weight subjects (including both sexes, BMI:  $24.1 \pm 2.9$ , age: 25~71), we estimated that the within-subject variation in RMR is less than 0.15 kcal/min, whereas our instrument variation is less than 0.05 kcal/min within a day. Therefore, using the same cross-sectional design of 15 patients per arm, assuming we can detect a difference in RMR of 0.14 kcal/min (which is more than two times of the instrument precision), we can achieve a sufficient power of 80% with a significance level of 0.05 using a one-sided two-sample t-test.

For the exploratory aims, we plan to assess if the response to ThyPRO-39, a QoL questionnaire/instrument would yield significant difference between subjects on LT4/LT3 vs LT4 alone. We are also interested in

assessing potential genetic heterogeneity underlying the treatment group effect. More specifically, we would model the QoL endpoints using the ANOVA models incorporating treatment effect (LT4/LT3 vs LT4 alone), Thr92Ala D2 polymorphism (Thr/Thr, Thr/Ala, vs Ala/Ala), and their interaction effects. This would depict a better picture of which genetic group might benefit the most from LT4/LT3 combo therapy. This ANOVA modeling strategy can be extended in a straightforward manner to ANCOVA to assessing changes in other outcomes of interest, adjusting for potential genetic heterogeneity, as well as serum T3 level, and other important covariates.

Notice that even if the primary endpoints are expressed as differences between baseline and end of the study, in the LT3/LT4 vs LT4 alone groups, we are collecting phenotypic data at each follow-up time point. This will offer great opportunities to characterize the longitudinal profiles of these phenotypic data and to estimate the effect size as well as the standard deviation over time, essentially the trajectory of these measured endpoints over the 6-month time period. Ultimately, this would help size a much more powerful study that analyzes the repeated measures of the phenotypic data, or design a sufficiently powered study with a limited number of subjects due to the elimination of inter-subject variation. For example, with 4 time points planned for the study, even if the power to assess the treatment effect difference on the weight loss of 1.4 (SD=1.9) is 62.7% given a sample size of 15 vs 15 (LT4/LT3 vs LT4 alone), the power to detect the treatment by time effect could range from 80% up to 95% depending on mean trajectory change, and the correlation structures between measurements at different time points from a repeated measures ANOVA/ANCOVA modeling. We believe this is a significant strength in our dense phenotyping approach with multiple time points, particularly in consideration of the exploratory scope of the R21 funding mechanism.

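### The LDL power table does not follow from its own column headings: with the SD in percent as headed, stated power is 10 to 15 points too high, while the figures fit an SD of 10 or 12 mg/dl

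*Combined protocol and SAP*

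**What the plan says.** The Endpoints list includes as secondary: "Differences in Lipid levels between LT4 alone or LT3/LT4 therapy". In the Statistical Methodology section, "power and sample size calculations for changes in lipids were based on our original cross-over study", and from the smaller expected rise in T3 "a 5% to 8% reduction in LDL or non-HDL for this study is hypothesized". The table is introduced with: "We also provide the sample size calculation and power estimation for the hypothesized percent reduction in LDL/non-HDL". The same sentence gives the LDL of the LT4 group as 122.6 ± 25.2 mg/dl.

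The table has rows for reductions of 5, 6, 7 and 8%, each at an SD of 10 and of 12 in a column headed SD (%). The left half gives power at 15 per arm: 49.7, 62.6, 74.2 and 83.5% at SD 10, and 39.9, 49.7, 60.5 and 70.5% at SD 12. The right half gives 34, 24, 18 and 14 per arm at SD 10, and 49, 34, 25 and 20 at SD 12, with power of 80.2 to 81.4%. The caption says: "The right columns indicate the sample size calculations necessary to assure an 80% power with a significance of 0.05".

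The test is specified just before the weight table, as a "two-sample, one-sided t-test based on weight loss in LT3/LT4 as compared to LT4 alone", "given a significance level of 0.05". The lipid calculation is introduced as being done similarly.

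**The concern.** When the reduction and its SD are both in percent, the standardised effect is simply their ratio. For 8% over 10% that is 0.80, and a one-sided t-test with 15 per arm then has clearly less than the 83.5% power printed.

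The table is the only statement in the documents of what 15 per arm can show for LDL. Its one row above 80% at that size (8%, SD 10) is the one a reader would take as support for the lipid endpoint. The right half could also be reused: someone sizing a later trial with a percent SD would recruit about a third too few patients (for example 34 instead of 51 per arm).

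**Working it through.** **Inputs.** One-sided alpha 0.05 and the two-sample t-test come from the text before the weight table. The 15 per arm, the reductions of 5 to 8%, the SDs of 10 and 12 and the LDL of 122.6 mg/dl come from the LDL table and the paragraph above it.

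**Formula.** With standardised effect d and n per arm, power = P(T > t(0.95; 2n−2)), where T is noncentral t with 2n−2 degrees of freedom and noncentrality d·√(n/2). The required n is the smallest giving at least 80%.

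**Step 1: check the method on the weight table.** For 1.4 kg with SD 1.9, d = 0.737. Power is 62.7% at n = 15; n for 80% is 24, with power 80.8%. All three are as printed. All ten weight rows reproduce in this way, so the method is the plan's own.

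**Step 2: LDL as headed, d = reduction (%) / SD (%).**

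| Reduction, SD | d | Power at 15: printed | Computed | Excess | n: printed | Power at printed n | n needed |
|---|---|---|---|---|---|---|---|
| 5%, 10% | 0.500 | 49.7 | 37.9 | 11.8 | 34 | 65.4 | 51 |
| 6%, 10% | 0.600 | 62.6 | 48.3 | 14.3 | 24 | 65.6 | 36 |
| 7%, 10% | 0.700 | 74.2 | 58.9 | 15.3 | 18 | 66.0 | 26 |
| 8%, 10% | 0.800 | 83.5 | 68.9 | 14.6 | 14 | 66.1 | 21 |
| 5%, 12% | 0.417 | 39.9 | 29.8 | 10.1 | 49 | 65.7 | 72 |
| 6%, 12% | 0.500 | 49.7 | 37.9 | 11.8 | 34 | 65.4 | 51 |
| 7%, 12% | 0.583 | 60.5 | 46.6 | 13.9 | 25 | 65.1 | 38 |
| 8%, 12% | 0.667 | 70.5 | 55.4 | 15.1 | 20 | 66.5 | 29 |

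No printed power at 15 per arm and no printed n is reproduced.

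**Step 3: other tests, still in percent.** None of these gives the printed table:
- A two-sided t-test gives 19.7 to 56.2% at 15 per arm.
- The one-sided normal approximation gives 30.7 to 70.7%.
- A one-sample (paired) t-test with n = 15 gives 45.6 to 90.3%.
- Expressing the effect as a log ratio gives 30.8 to 72.0%.
- One-sided alpha 0.10 comes near some cells but misses others by up to 3.9 points, and contradicts the stated 0.05.

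**Step 4: solve for the SD.** The SD implied by the printed powers is about 8.16% in the first four rows and 9.79% in the last four (apart from the 39.9 cell). Multiplying by 1.226 gives 10.0 and 12.0 mg/dl.

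**Step 5: LDL in mg/dl, d = reduction (%) × 1.226 / SD (mg/dl).** The reductions become 6.13, 7.36, 8.58 and 9.81 mg/dl.
- SD 10: power at 15 per arm is 49.7, 62.6, 74.2 and 83.5%; n is 34, 24, 18 and 14.
- SD 12: power is 39.0, 49.7, 60.5 and 70.5%; n is 49, 34, 25 and 20.

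All eight sample sizes, all eight right-hand powers and seven of the eight left-hand powers match. The exception is 5% at SD 12, where d = 0.511 and power is 38.98%, against 39.9 printed.

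**Step 6: detectable reduction.** At 15 per arm, 80% power needs d = 0.9307.
- SD in percent: 0.9307 × 10 = 9.3% and 0.9307 × 12 = 11.2%.
- SD in mg/dl: 9.307/1.226 = 7.6% and 11.168/1.226 = 9.1%.

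**The case against.** The simplest explanation is a wrong unit in one column heading. Since 23 of 24 figures match an SD in mg/dl, the calculation was probably done in mg/dl, and the loss of 10 to 15 points applies only if the heading is right. The introductory sentence supports this: it supplies the LDL of 122.6 mg/dl, which a percent-over-percent calculation would not need. This stands as evidence of how the reduction was converted. It does not settle whether an SD of 10 mg/dl was intended, or whether an SD of 10% was intended and left unconverted.

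The practical consequence is also modest. The sample size is fixed by time and funding. Seven of the eight LDL rows already show less than 80% power at 15 per arm. Section 4 says a later trial will be sized on the pilot's own estimates. Lipid metabolism is a tertiary objective, although lipid levels are listed as a secondary endpoint. All of this stands and limits the weight of the point, but the table remains wrong as printed.

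Two smaller points are fair. The one-sided t-test is stated for weight and only carried over to LDL by the linking word, though the exact match in mg/dl supports that reading. The single cell of 39.9 against 39.0 is trivial and may be a typing slip.

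**Conclusion.** The concern holds. With the SD in percent as headed, power at 15 per arm is overstated by 10.1 to 15.3 points. The printed sample sizes give about 65 to 66% power, and the 83.5% row falls to 68.9%. No reduction in the hypothesised 5 to 8% range then reaches 80% power.

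With the SD in mg/dl, the powers and sample sizes stand apart from one cell, but the heading is wrong.

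Under either reading the SDs have no stated source. The text names the earlier cross-over study as the basis but does not give its SD of LDL change. The only LDL SD in the section is the 25.2 mg/dl for the LT4 group, which I read as a between-patient SD. An SD of change can well be smaller, but 10 and 12 mg/dl are only 8.2% and 9.8% of 122.6 and need support.

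The result rests on the one-sided two-sample t-test at 0.05 with equal arms. That the calculation used mg/dl is inferred from the match; the documents do not say so.

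**What to change.** State one unit for the SD, and then do one of the following.

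- **Keep percent.** Replace the power at 15 per arm with 37.9, 48.3, 58.9 and 68.9% (SD 10%) and 29.8, 37.9, 46.6 and 55.4% (SD 12%). Replace the sample sizes with 51, 36, 26 and 21 (power 80.6, 80.9, 80.1 and 81.7%) and 72, 51, 38 and 29 (power 80.0, 80.6, 80.9 and 80.6%).
- **Use mg/dl.** Relabel the column SD (mg/dl), change 39.9 to 39.0, and say that the reduction was converted using 122.6 mg/dl.

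In both cases, add a sentence saying whether the SD is an SD of change and where it comes from, set against the 25.2 mg/dl already quoted, and naming the test used for LDL.

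The first option costs a recalculated table with less favourable stated power; the second costs a heading, one cell and a sentence or two. Neither changes enrolment or study conduct.

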
### 3.3 Aim 3: To characterize the changes in lipid metabolism following thyroidectomy.

Thyroid hormone exerts pervasive actions on lipid metabolism by directly regulating transcription of the LDL receptor, intracellular metabolism of cholesterol within the hepatocyte, cholesterol excretion and reabsorption through the biliary tract, and peripheral lipolysis (10, 76). Hypothyroidism results in significant, reversible hypercholesterolemia, which in turn contributes to increased cardiovascular risk. We have previously demonstrated that the increase in circulating levels of T3 following substitution of LT3 for LT4 results in significant decrease in total and LDL cholesterol, 10.9% and 13.3%, respectively (40). No significant differences in cholesterol or in lipoprotein levels were demonstrated as a result of LT3/LT4 therapy, presumably because of the heterogeneity of the study populations. Our study design offers the

unique opportunity to assess the effects of LT3/LT4 combination therapy in patients who transitioned from euthyroidism to hypothyroidism without the confounder of residual thyroid hormone production or a prolonged course of thyroid dysfunction. We will compare the levels of total, LDL, and HDL cholesterol at baseline and at three and six months following surgery between LT4 and LT3/LT4-treated patients. Additionally, by longitudinally assessing serum lipids in the same patient before and after thyroidectomy while on LT4 or LT3/LT4 therapy, we will be able to obtain information whether surgical hypothyroidism, despite adequate replacement results in significant changes in lipid levels, and if LT3/LT4 therapy this can be prevent these changes. The data gathered in this aim will thus provide high value (due to the strengths of the study design) point estimates to evaluate the effect size of the LT3/LT4 on lipid metabolism. **Expected results.** We predict that the LT3/LT4 therapy will result in a measurable decrease in total and LDL cholesterol compared to LT4 treatment arm, which in turn will show an increase compared to baseline.

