## **4 STUDY DESIGN**

This is a two arm, parallel, double blind placebo controlled (both arms will receive active medication) proof of concept study. Thirty patients will be enrolled and allocated 1:1 to the LT4 alone or to the LT3/LT4 combination regimen. Due to the exploratory and preliminary nature of the funding mechanism (R21) and FOA (Pilot and Feasibility Clinical Trials in Diabetes, and Endocrine and Metabolic Diseases), the study is geared toward gathering a large amount of preliminary data in a relatively small number of study participants (dense phenotyping). The acquisition of point estimates of the endpoints will then enable us to 1) justify the execution of a large study (go/no-go); 2) define primary and secondary outcomes; 3) adequately power a large, multicenter study able to demonstrate clinically relevant differences in the selected endpoints.

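### The LDL power table rests on SDs of 10 and 12 mg/dl that have no stated source and match the plan's own LDL SD of 25.2 mg/dl only if LDL correlates about 0.88 to 0.92 over time

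*Combined protocol and SAP*

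**What the plan says.** The LDL table stands in the Protocol Summary under Statistical Methodology, after the weight table. It is said to give sample size and power "for the hypothesized percent reduction in LDL/non-HDL given the LDL of $122.6 \pm 25.2$ (mg/dl) for LT4 group". The effect column is the percentage "reduction in LDL LT3/LT4 vs LT4", and the text states that "a 5% to 8% reduction in LDL or non-HDL for this study is hypothesized". The SD column is headed as a percentage and holds 10 and 12.

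At 15 per arm the printed power for 5, 6, 7 and 8% is 49.7, 62.6, 74.2 and 83.5% with SD 10, and 39.9, 49.7, 60.5 and 70.5% with SD 12. The printed sizes per arm for 80% power are 34, 24, 18 and 14, and 49, 34, 25 and 20.

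The lipid paragraph says its calculations concern changes in lipids, are done in the same way as those for weight, and rest on the earlier crossover study. From that study it reports percentage reductions in LDL and non-HDL, but no SD of LDL change.

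The endpoint list makes lipids secondary and words the endpoint as a between-arm difference in lipid levels. Section 3.3, speaking of the trial's patients, says: "We will compare the levels of total, LDL, and HDL cholesterol at baseline and at three and six months following surgery between LT4 and LT3/LT4-treated".

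**The concern.** A reader told that the calculation takes LDL as 122.6 ± 25.2 mg/dl would expect 25.2, or something derived from it, to be the SD behind the table. It is the only LDL SD in the documents. The values used are smaller by a factor of 2.1 (25.2/12) to 2.5 (25.2/10), and nothing explains the step.

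What is at stake is how far the printed LDL power can be relied on: up to 83.5% at 15 per arm, and as few as 14 per arm for 80%. If the true SD is larger, a null LDL result could be over-read as evidence against a 5 to 8% effect that the trial had little chance of detecting.

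**Working it through.** **Inputs**
- Test: "two-sample, one-sided t-test based on weight loss in LT3/LT4 as compared to LT4 alone", stated for weight and carried over to lipids.
- Design and alpha: "two-arm, randomized, cross-sectional design, given a significance level of 0.05".
- Size: "Thirty patients will be enrolled and allocated 1:1 to the LT4 alone or to the LT3/LT4 combination regimen", so 15 per arm and 28 degrees of freedom.
- Target for the size columns: "The right columns indicate the sample size calculations necessary to assure an 80% power with a significance of 0.05".
- LDL in the LT4 group: mean 122.6, SD 25.2 mg/dl; 25.2/122.6 = 20.6%.
- Effects of 5, 6, 7 and 8% of 122.6: 6.13, 7.36, 8.58 and 9.81 mg/dl.

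Power is from the noncentral t with noncentrality (difference/SD) × √(15/2). Size per arm is the smallest n whose power reaches 80%.

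**Step 1: reproduce the printed table**

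| SD used | Power at 15 per arm (5, 6, 7, 8%) | n per arm for 80% |
|---|---|---|
| 10 mg/dl | 49.7, 62.6, 74.2, 83.5 | 34, 24, 18, 14 |
| 12 mg/dl | 39.0, 49.7, 60.5, 70.5 | 49, 34, 25, 20 |
| 10% (12.26 mg/dl) | 37.9, 48.3, 58.9, 68.9 | 51, 36, 26, 21 |
| 12% (14.71 mg/dl) | 29.8, 37.9, 46.6, 55.4 | 72, 51, 38, 29 |

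Read in mg/dl, all eight sizes match and seven of eight powers match to 0.1. The exception is 5% with SD 12: 39.0, printed as 39.9. Read as percent, as the column is headed, no entry matches. The effect was therefore converted to mg/dl with 122.6, while the SD was entered as 10 or 12 mg/dl (8.2% or 9.8% of the mean).

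**Step 2: SD 25.2, if follow-up levels are compared**

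Standardised effects run from 6.13/25.2 = 0.243 to 9.81/25.2 = 0.389. Power is 16.0, 19.4, 23.1 and 27.3%. The sizes for 80% are 210, 146, 108 and 83 per arm.

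**Step 3: correlation implied by 10 and 12 mg/dl, if change or a baseline-adjusted value is analysed**

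With equal variances at baseline and follow-up, the SD of change is 25.2 × √(2(1 − r)), so r = 1 − SD²/(2 × 25.2²). The baseline-adjusted SD is 25.2 × √(1 − r²), so r = √(1 − SD²/25.2²).
- SD 10: r = 1 − 100/1270.08 = 0.921 for change; 0.918 adjusted.
- SD 12: r = 1 − 144/1270.08 = 0.887 for change; 0.879 adjusted.

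**Step 4: power over a range of r**

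The documents give no r, so these values are assumptions.

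| r | SD of change (mg/dl) | Change-score power, 5 to 8% | Adjusted SD (mg/dl) | Adjusted power, 5 to 8% |
|---|---|---|---|---|
| 0.5 | 25.2 | 16.0 to 27.3 | 21.8 | 18.6 to 32.9 |
| 0.7 | 19.5 | 21.0 to 38.1 | 18.0 | 23.1 to 42.5 |
| 0.8 | 15.9 | 26.9 to 50.0 | 15.1 | 28.7 to 53.5 |
| 0.9 | 11.3 | 42.4 to 75.2 | 11.0 | 43.9 to 77.1 |
| 0.92 | 10.1 | 49.2 to 83.0 | 9.9 | 50.5 to 84.3 |

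**The case against.** The strongest reply is that 25.2 is a between-person SD of the LDL level and was never meant as the SD of the test. The lipid paragraph speaks of changes and models itself on the weight calculation. There the plan used the SD of weight change (1.9 kg), not the SD of body weight (12.5 kg). Putting 12.5 kg into the weight table would give about 9 to 12% power instead of 62.7 to 92.6%, which is clearly not the plan's method. On this view 122.6 only converts percentages to mg/dl, and the crossover study, a within-patient design, supplied 10 and 12.

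Much of this stands. A reader might infer that the LDL power simply is 16 to 27%, or that the SD is too small by about half. The documents do not support either as a flat statement. Those figures hold for a comparison of levels, or for change scores at r = 0.5, and the text leaves the analysed quantity open. Nor do the documents show that a correlation near 0.9 is implausible. A mean shift in LDL after surgery does not by itself lower the correlation; patients enter euthyroid, doses are titrated towards baseline TSH, and statin treatment is held constant.

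A reader might also infer that the follow-on trial would be badly undersized. The plan says otherwise: the pilot's own effect estimates and SDs are to size that trial, not this table.

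The reply does not supply the missing number. For weight the plan prints the SD of change and its source. For LDL it prints only percentage reductions and one SD, 25.2, which the table does not use. The wording of the endpoint and of Section 3.3 can still be read as a comparison of levels.

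**Conclusion.** The point holds as one about an unsourced assumption and a mislabelled column. Apart from the 39.9% entry, the arithmetic is sound once the SDs are taken as 10 and 12 mg/dl.

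The plan's stated inputs support the printed LDL figures only if change or a baseline-adjusted value is analysed and the correlation is about 0.92 (SD 10) or 0.88 to 0.89 (SD 12). Up to r = 0.8, power for the largest hypothesised effect is at most 50% for change and 53.5% with baseline adjustment. At r = 0.9 it is 75 to 77%, above the printed SD 12 figure of 70.5% but below 83.5%. For a comparison of levels it is 27.3%. Under the table's own percentage label it is 68.9% (SD 10%) or 55.4% (SD 12%).

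These results assume a one-sided t-test at 0.05, 15 analysed per arm, and equal LDL variance at baseline and follow-up. LDL is a secondary endpoint and 30 patients was fixed by time and funding, so what needs correcting is the stated power, not the design.

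**What to change.** 1. State whether the LDL and non-HDL analysis is of the follow-up level, the change from baseline, or a baseline-adjusted value, and at which visit.
2. Replace 10 and 12 with the SD of within-patient LDL change from the crossover study, naming that source. Failing that, use SDs derived from 25.2 mg/dl at stated correlations, for example 0.5, 0.7, 0.8 and 0.9.
3. Give the SD column its correct unit, and correct 39.9% to 39.0% if that row stays.
4. Recompute both halves of the table. Keep 83.5% and 14 per arm only if the sourced SD supports them.

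The cost is one recomputed table and a sentence or two of text, with no extra patients and no change to visits or procedures. The stated LDL power will probably be less favourable unless the crossover SD bears out the present values.

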5.1.4 Age 18-89 years of age

5.1.5 Males and females

## **5.2 Exclusion Criteria**

A potential subject who meets any of the following exclusion criteria is ineligible to participate in the study.

- 5.2.1 Weight <50 or >150 Kg;
- 5.2.2 Graves' disease
- 5.2.3 Use of thyroid hormone therapy use of thyroid hormone therapy or thyroid supplements (at screening) except for multinodular goiter;
- 5.2.4 Indication for thyroid hormone suppressive therapy following surgery
- 5.2.5 Uncontrolled arterial hypertension. (Stage 2 or greater on medication); (>140/90 mmHg at screening while on medication (patients with hypertension controlled by therapy will be allowed to participate)).
- 5.2.6 Cardiovascular disease: congestive heart failure; unstable coronary artery disease (angina, coronary event, or revascularization within 6 months); atrial fibrillation, arrhythmia or ventricular arrhythmia,
- 5.2.7 Pregnancy, breastfeeding, or planned pregnancy within six months from the thyroidectomy
- 5.2.8 History of major depression or psychosis;
- 5.2.9 Uncontrolled diabetes (HbA1c > 8% or fructosamine < 325 mcmol/l in substitution of HbA1c to reflect recent improvement in diabetes control at screening
- 5.2.10 Conditions that in the opinion of the PI may impede the successful completion of the study

Patients on statin treatment will be allowed to participate in the study and the treatment will remain unchanged throughout the study.

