## Appendix A

**BMR formula** is as follows:

BMR (kcal / day) = 10 \* weight (kg) + 6.25 \* height (cm) – 5 \* age (y) + s (kcal / day) , where s is +5 for males and -161 for females.

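### The 80% power for energy expenditure uses a bound on within-subject variation as the SD of a between-arm comparison; for change from baseline, power could be as low as about 55%

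*Combined protocol and SAP*

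**What the plan says.** Energy expenditure is one of two primary endpoints (Protocol Summary, Endpoints). Its power is treated in one paragraph of the Statistical Methodology. From a pilot in 12 healthy volunteers of normal weight, the plan reports that "we estimated that the within-subject variation in RMR is less than 0.15 kcal/min", with instrument variation below 0.05 kcal/min within a day. It continues: "using the same cross-sectional design of 15 patients per arm, assuming we can detect a difference in RMR of 0.14 kcal/min", and concludes that "we can achieve a sufficient power of 80% with a significance level of 0.05 using a one-sided two-sample t-test".

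The weight calculation earlier in the section is likewise framed as giving "required sample sizes in a two-arm, randomized, cross-sectional design, given a significance level of 0.05". A later paragraph, however, describes the endpoints as changes: "even if the primary endpoints are expressed as differences between baseline and end of the study".

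The section also says that no earlier study has measured change in energy expenditure by whole-room calorimetry in a comparable population. It gives no SD of change in RMR, no between-patient SD and no correlation between visits.

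**The concern.** A two-sample t-test needs the SD, across patients within an arm, of whatever is compared between arms. The plan supplies an upper bound on a different quantity, variation within a subject. It does not say whether that is the SD of a single visit or of the difference between two visits.

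There are two readings of the comparison, and neither supports an unconditional 80%:

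- **Change from baseline.** The difference of two visits carries error from both, plus any real variation in response between patients.
- **Follow-up values only**, as the word cross-sectional may suggest. Between-patient differences in RMR then enter the SD in full, and the calculation leaves them out.

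What is at stake is how a non-significant result would be read. The plan reports no significant difference in resting energy expenditure in the earlier crossover, even with full LT3 substitution, so such a result is plausible here. Someone told that power was 80% would count it as evidence against an effect of 0.14 kcal/min, which is 0.14 × 1440 = 202 kcal/day.

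**Working it through.** **Inputs.** From the Statistical Methodology: difference 0.14 kcal/min, 15 per arm, one-sided 0.05, two-sample t-test (28 df), within-subject variation below 0.15, instrument variation below 0.05. From Appendix A: 10 kcal/day per kg, and the sex constants.

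**Method.** Power from the noncentral t distribution with noncentrality δ / (SD × √(2/15)). This reproduces all ten 15-per-arm powers in the plan's weight table (for example 1.4/1.9 gives 62.7%, 1.8/1.9 gives 81.2%, 1.4/2.3 gives 49.3%), so it is the plan's own method for weight.

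**Step 1: reproduce the 80%.** With SD 0.15, the noncentrality is 0.14 / (0.15 × 0.365) = 2.56 and power is 80.2%. Solving backwards, exactly 80% needs SD 0.1504, a standardised difference of 0.931. The instrument figure of 0.05 gives more than 99.9%. The two figures combined, √(0.15² + 0.05²) = 0.158, give 76.4%. Only 0.15, taken as the SD of the between-arm comparison, yields the stated power.

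**Step 2: change from baseline, if the figure is a single-visit SD s.** With independent visit errors and no variation in response, the SD of change is √2 × s. Values of s below 0.15 are illustrations; the plan gives only the bound.

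| s (kcal/min) | SD of change | Power for 0.14 |
|---|---|---|
| 0.15 (bound) | 0.212 | 54.7% |
| 0.14 | 0.198 | 59.7% |
| 0.13 | 0.184 | 65.2% |
| 0.12 | 0.170 | 71.2% |
| 0.10 | 0.141 | 84.1% |

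The break-even is s = 0.1504/√2 = 0.106, about 29% below the bound. At s = 0.15, the difference detectable with 80% power is 0.931 × 0.212 = 0.197 kcal/min, or 284 kcal/day.

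**Step 3: change from baseline, if 0.15 is already the SD of repeat-visit differences.** Power is 80.2% if true response is the same in every patient. For an assumed response SD r, the SD of change is √(0.15² + r²): r = 0.05 gives 76.4% and r = 0.10 gives 66.6%.

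**Step 4: follow-up values only.** The largest between-patient SD that keeps 80% is √(0.1504² − w²), where w is the within-subject SD. This is 0.011 kcal/min at w = 0.15, 0.091 at 0.12 and 0.112 at 0.10. At the bound, 0.011 × 1440 is about 16 kcal/day. By the Appendix A formula that equals 1.6 kg of body weight. The sex term alone, "where s is +5 for males and -161 for females", separates men and women by 5 + 161 = 166 kcal/day (0.115 kcal/min). Section 5.1 admits both sexes, and Section 5.2 excludes only "Weight <50 or >150 Kg".

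**The case against.** The strongest reply is that the sum is correct and that 55% is the worst case of one reading. It requires 0.15 to be a single-visit SD, the true value to sit at a figure the plan calls an upper limit, and the visit errors to be independent. The weight calculation also gives some support to the other reading: its SD of 1.9 kg comes from a within-patient change in the earlier crossover, so entering a change SD in the two-sample test may be the sponsor's habit. On that view, cross-sectional simply means one two-sample comparison of changes, fixed differences in weight and sex cancel, and Step 4 does not apply. Finally, Section 3.1 says the ventilated hood misses small differences, so the crossover's null result does not transfer directly; this is a pilot meant to yield point estimates, and no decision depends on the 80%.

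Much of this stands. The fault lies in the input, not the arithmetic. Step 4 is the weaker branch, and 55% is the bottom of a range. The plan's remark about how to "design a sufficiently powered study with a limited number of subjects due to the elimination of inter-subject variation" concerns a future trial, although it does tie the removal of between-patient variation to repeated-measures analysis.

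The reply still does not rescue the statement as written. The weight precedent does not establish what the RMR figure is. An upper bound on one variance component does not bound the SD the test needs. Even the favourable reading holds 80% only if response does not vary between patients. Weight and LDL each have power tables over two SDs; this primary endpoint has a single unconditional figure.

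**Conclusion.** The concern holds. The 80% comes from using a bound on within-subject variation, estimated in healthy volunteers, as the SD of a between-arm comparison whose endpoint is change from baseline. Depending on what 0.15 represents, power for 0.14 kcal/min runs from about 55% (single-visit SD at the bound) to above 80% (single-visit SD below about 0.106). The stated 80% survives if 0.15 is the SD of repeat-visit differences and response does not vary. The figures assume independent visit errors and, unless stated otherwise, no variation in response; such variation would lower them. Funding set the sample size and no decision rule uses the 80%, so this is a reporting correction that should be made, not a reason to redesign the trial.

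**What to change.** In the energy-expenditure paragraph of the Statistical Methodology, replace the unconditional power statement with:

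1. what statistic 0.15 kcal/min is, taken from the pilot data;
2. the SD of change from baseline that follows from it;
3. power for 0.14 kcal/min as a range over that SD.

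If 0.15 is a single-visit SD, report about 55% at 0.15, 60% at 0.14, 71% at 0.12 and 84% at 0.10, before any variation in response, and say that at the bound 80% power applies only to a difference of about 0.20 kcal/min. If it is the SD of repeat-visit differences, say so and keep the 80%, on the condition that response does not vary between patients. If the sponsor prefers a baseline-adjusted analysis, it should compute that power from its own pilot SDs.

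Reconcile the cross-sectional wording in the weight and energy-expenditure calculations with the baseline-to-end definition of the primary endpoints.

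The cost is one look-up in the pilot data and a few sentences of text. The reported power may be less favourable. No patients or procedures are added.
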